2.2 BACKGROUND

Immune-mediated thrombotic thrombocytopenic purpura (also known as aTTP) is a life-threatening, thrombotic microangiopathy characterized by severe thrombocytopenia, microangiopathic hemolytic anemia, and organ ischemia. It is an ultra-orphan disease with an annual incidence reported to be about 3 cases per million people in the US (6, 7).

It is caused by inhibitory autoantibodies to vWF-cleaving enzyme ADAMTS13 that result in a severe deficiency in the activity level of the enzyme. Severe deficiency (<10%) of ADAMTS13 enzyme activity has been recognized as a biomarker specific for iTTP and is used in the acute and long-term management of patients with iTTP (8).

Von Willebrand factor, a key protein in hemostasis, plays a pivotal role in the recruitment of platelets to sites of vascular injury. More than 90% of circulating vWF is expressed by endothelial cells and secreted into the systemic circulation as ultra-large vWF (ULvWF) multimers. Under high shear stress conditions such as in arterioles and capillaries, the platelet-binding A1 domain of the ULvWF multimers interact spontaneously with the glycoprotein Ib-IX-V receptor on platelets. In healthy individuals, ULvWF multimers are immediately cleaved into smaller, regular-sized multimers by the vWF-cleaving protease ADAMTS13. This prevents ULvWF interaction with platelets and limits microthrombus formation. When there is severe ADAMTS13 deficiency, ULvWF released from the endothelium are not cleaved appropriately, leading to vWF-dependent platelet aggregation eventually resulting in microvascular thrombosis (9). The consumption of platelets in these microthrombi results in thrombocytopenia, one of the clinical feature of iTTP, and may present with muco-cutaneous bleeding symptoms such as epistaxis, bruising, petechiae, hematuria, and gastrointestinal bleeding (10, 11).

Prior to the availability of caplacizumab, episodes of iTTP were associated with an acute mortality of 10–20% and thromboembolic morbidities such as myocardial infarction and cerebrovascular accident. In addition, tissue ischemia caused by microvascular thrombosis may result in multiorgan dysfunction including renal dysfunction. Most patients have very high levels of lactate dehydrogenase (LDH) as a result of the combination of hemolysis and tissue ischemia. Elevations of serum troponin I and troponin T are common (12, 13).

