3.3 SECONDARY ENDPOINTS ANALYSIS

Secondary **efficacy** endpoints analyses are defined in this section.

Secondary **safety** endpoints analyses are defined in [Section 3.6.2](#) (AE, serious AE [SAE], AE of special interest [AESI]) and [Section 3.6.3](#) (clinical safety laboratory variables, vital signs, and electrocardiogram [ECG]).

The main analysis approach for the secondary efficacy endpoints will be to analyze the endpoints on the mITT population, ie, all enrolled participants who received at least 1 dose of IMP and with an ADAMTS13 activity of <10% at baseline.

Secondary endpoints listed below will be analyzed using the count and percentage of participants. Two-sided 95% CIs will be provided.

- Proportion of participants achieving remission during the overall study period.
- Proportion of participants who require TPE during the on-treatment period.
- Proportion of participants achieving Clinical Response during on-treatment period and during the overall study period.
- Proportion of participants refractory to therapy during the on-treatment period.
- Proportion of participants with iTTP-related death during the on-treatment period and during the overall study period.
- Proportion of participants with a clinical exacerbation of iTTP during the on-treatment period and during the overall study period.
- Proportion of participants with a clinical relapse of iTTP during the on-treatment period and during the overall study period.

For the following time to event endpoint, median time to event (with 2-sided 95% CI) as well as Q1 and Q3 will be estimated using Kaplan-Meier estimates, and survival curve provided.

- Time to platelet count response, defined as time from start of treatment to initial platelet count $\geq 150 \times 10^9/L$ that is sustained for ≥ 2 days.

[figure not shown]
The percentage of event at the following timepoints during the on-treatment period, will be also provided: Day 1, Day 2, Day 3, Day 4, Day 5, Week 1, Week 2, Week 3, Week 4, Week 8, and Week 12.

[figure not shown]
More details regarding the definition and derivation of these endpoints are provided in [Section 5.4](#).

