- The values resulting from these derivations will be the values used for the graphical representation of platelet, LDH and ADAMTS13 activity from Day 4.

Consecutive laboratory assessments are considered as 'consecutive visits' for efficacy endpoints.

A participant could potentially have missing laboratory assessment data, however, remission could still be confirmed at a subsequent laboratory value. In the case there is inadequate information to determine the remission status of a participant by the end of the study, the participant will be treated as not having achieved remission.

Clinical evidence of new or progressive ischemic organ injury

Clinical evidence of new or progressive ischemic organ injury is defined as any presence of following clinically significant iTTP event:

- Neurological event
- Elevated cardiac troponins
- Acute myocardial infarction
- Conduction abnormality
- Repolarization abnormality
- Heart failure
- Clinically significant renal event

which will be identified from the checkboxes in the "Clinically Significant TTP Event" eCRF form.

Exacerbation of TTP, Relapse of TTP and Other event will not be considered as clinical evidence of new or progressive ischemic organ injury.

Sustained Clinical Response

Sustained Clinical response is defined by the concomitance of the 3 following criteria for at least 2 consecutive visits (starting from D2):

- platelet count $\geq 150 \times 10^9/L$
- LDH $< 1.5 \times ULN$
- no clinical evidence of new or progressive ischemic organ injury

Remission

Remission is defined as (1) a sustained Clinical response (see above) associated with (2) Clinical remission or (3) Complete ADAMTS13 Remission, whichever occurs first, and defined as:

- Clinical remission: No TPE (*Plasma Exchange* form) and no anti-VWF therapy (Caplacizumab treatment) for ≥ 30 days (from the date that Clinical Response is achieved).
- Complete ADAMTS13 Remission: The attainment of ADAMTS13 activity level $\geq 50\%$ for at least 2 consecutive visits (starting from D2).

Time to event

For each of below time to event, in case of no observation of the event or death, the censoring date will be defined as the last non-missing value of the analyzed parameter (platelet count, LDH....) if any, else as the start date of treatment (defined as first caplacizumab administration [whatever marketed or study IMP]).

- Time to platelet count response will be calculated as follow:

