Date of initial day of 2 consecutive days where platelet count $\geq 150 \times 10^9/L$ - Date of start of treatment

- Time to LDH $\leq 1 \times$ ULN will be calculated as follow:
Date where LDH $\leq 1 \times$ ULN for the first time - Date of start of treatment
- Time to serum creatine $\leq 1 \times$ ULN will be calculated as follow:
Date where serum creatine $\leq 1 \times$ ULN for the first time - Date of start of treatment
- Time to cardiac troponin I $\leq 1 \times$ ULN will be calculated as follow:
Date where serum creatine $\leq 1 \times$ ULN for the first time - Date of start of treatment
- Time to ADAMTS13 partial remission (ADAMTS13 activity between 20% [included] and lower limit of normal [LLN] [excluded]) at 2 consecutive visits after clinical response will be calculated as follow:
Date of initial day of 2 consecutive visits after clinical response with ADAMTS13 partial remission - Date of start of treatment
- Time to normalization of ADAMTS13 level defined as sustained ADAMTS13 level of $\geq 50\%$ at 2 consecutive visits after clinical response will be calculated as follow:
Date of initial day of 2 consecutive visits after clinical response with normalization of ADAMTS13 level - Date of start of treatment
- Time to reduction of anti-ADAMTS13 antibodies below the threshold of positivity (12 U/mL) will be calculated as follow:
Date of reduction of anti-ADAMTS13 antibodies below the threshold of positivity - Date of start of treatment

Refractory to therapy

Refractory to the therapy during the on-treatment period is defined as following:

- Lack of platelet count increment (over 2 consecutive days),
OR
- platelet counts $<50 \times 10^9/\text{L}$ AND LDH $>1.5 \times \text{ULN}$ despite 5 days of treatment.

Note: if the 2 consecutive values of platelet are the same, the condition is not met for refractory. Additionally, a patient can become refractory after a sustained platelet count response if he still is on therapy.

iTTP-related death during the on-treatment period and during the overall study period

The iTTP-related deaths will be derived from the ***Clinically Significant iTTP Event*** form with the ***Outcome*** field filled as Fatal.

Clinical Exacerbation

Clinical exacerbation is defined between a Clinical Response and a Clinical Remission as:

- platelet count decreases to $<150 \times 10^9/\text{L}$ (note that it is assumed that other causes of thrombocytopenia are excluded from the data collected in the database),

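### Time to platelet response: participants who die first appear to be censored at their last laboratory value, which would overstate the Kaplan-Meier response curve by about 1 to 2 points per death

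*SAP*

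**What the plan says.** SAP 5.4 (Appendix 4, Time to event) introduces its rule with "For each of below time to event" and then states: "in case of no observation of the event or death, the censoring date will be defined as the last non-missing value" of the parameter concerned. If no such value exists, the censoring date is the start of treatment. The list that follows covers platelet response, LDH, creatinine, troponin, two ADAMTS13 activity endpoints and anti-ADAMTS13 antibodies. Every event date in it is a laboratory date. For platelet response it is "Date of initial day of 2 consecutive days where platelet count" reaches the threshold, minus the start date. Death enters none of the formulas.

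For time to platelet count response, SAP 3.3 specifies that "median time to event (with 2-sided 95% CI) as well as Q1 and Q3 will be estimated using Kaplan-Meier estimates", with a curve. It adds: "The percentage of event at the following timepoints during the on-treatment period", and lists Days 1 to 5 and Weeks 1, 2, 3, 4, 8 and 12. Protocol 9.2.3 also names Kaplan-Meier. No competing-risk method and no separate rule for deaths appears in the readable text.

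Remission is handled differently. Under SAP 5.4, a participant whose status cannot be determined by the end of the study counts as not in remission.

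**The concern.** Kaplan-Meier censoring assumes that a censored participant could still have the event, at the same rate as those who remain at risk. A participant who dies with a low platelet count cannot. Once that participant leaves the risk set, the lost weight passes to those who respond later. The curve then estimates response in a hypothetical population without deaths, not the share of treated participants who responded.

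The error can only favour the treatment. The two estimators agree until the first response after a censored death, and Kaplan-Meier is higher from then on. The trial withholds first-line plasma exchange, so a death before platelet response is an outcome that the curve ought to show as a failure. The SAP is also uneven here: the same participant would be a failure for remission and merely censored for platelet response.

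**Working it through.** **Inputs.** N = 55 is the mITT target in SAP 4. The plan states no figure for the time-to-event endpoints. Its only precision figure concerns the primary endpoint, and it reproduces: the 95% Wilson lower bound for 39/55 responders is (0.7091 + 0.0349 − 0.1250)/1.0698 = 57.9%, against the stated 58%.

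The documents do not give the number or timing of deaths before response; both are assumed below. To place response times, I took a lognormal distribution with median 3 days and log-SD 0.5. The median follows the 2.97 days that Protocol 2.3.2 reports for the caplacizumab group of the Phase 2 trial; the log-SD is assumed.

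**Formulas.** Let d participants die before response, all with the same last platelet value date. Let r be the number who responded by that date, and m the number of living participants who never respond and are followed to Week 12.

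- Kaplan-Meier plateau, deaths censored: 1 − [(55 − r)/55] × [m/(55 − r − d)]
- Aalen-Johansen plateau, death competing: (55 − d − m)/55

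**Every survivor responds (m = 0).** Kaplan-Meier ends at 100% whatever d is.

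| Deaths | Aalen-Johansen | Excess (points) |
|---|---|---|
| 1 | 54/55 = 98.2% | 1.8 |
| 2 | 53/55 = 96.4% | 3.6 |
| 4 | 51/55 = 92.7% | 7.3 |

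**Five living non-responders (m = 5).**

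| Deaths | Last value | r | Kaplan-Meier | Aalen-Johansen | Excess (points) |
|---|---|---|---|---|---|
| 1 | Day 1 | 1 | 1 − (54/55)(5/53) = 90.7% | 49/55 = 89.1% | 1.6 |
| 1 | Day 5 | 41 | 1 − (14/55)(5/13) = 90.2% | 49/55 = 89.1% | 1.1 |
| 2 | Day 1 | 1 | 1 − (54/55)(5/52) = 90.6% | 48/55 = 87.3% | 3.3 |
| 2 | Day 5 | 41 | 1 − (14/55)(5/12) = 89.4% | 48/55 = 87.3% | 2.1 |
| 3 | Day 1 | 1 | 1 − (54/55)(5/51) = 90.4% | 47/55 = 85.5% | 4.9 |
| 3 | Day 5 | 40 | 1 − (15/55)(5/12) = 88.6% | 47/55 = 85.5% | 3.1 |

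The excess is therefore about 1 to 2 points per death.

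**Earlier timepoints.** Take 3 deaths with last value on Day 2, and m = 0. There are 11 responses by Day 2, 44 by Day 5 and 50 by Day 7.

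- Day 5: 1 − (44/55)(8/41) = 84.4%, against 44/55 = 80.0%
- Day 7: 1 − (44/55)(2/41) = 96.1%, against 50/55 = 90.9%

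**Median.** In the last example it is 3.04 days by Kaplan-Meier and 3.11 days by cumulative incidence. Across the cases with 1 to 3 deaths the shift stays below 0.1 day.

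**A shortcut that fails.** Some analysts keep the dead in the Kaplan-Meier risk set as non-responders to the end of follow-up. This matches Aalen-Johansen only if no living participant is censored early, and SAP 5.4 allows such censoring. Suppose 2 die early, 40 respond by Day 5, 5 living participants are then censored, and the remaining 8 respond. Aalen-Johansen gives 40/55 + 13/55 = 96.4%. The shortcut gives 1 − (15/55)(2/10) = 94.5%, which is biased the other way.

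**The case against.** **Wording.** The censoring sentence can be parsed as covering a single case, in which neither the event nor death is observed. The SAP would then not censor deaths but leave them without a rule. This cannot be excluded. The reading in which death is itself a reason for censoring is better supported, because no event date includes death and no other rule for deaths is given. The sentence needs repair either way.

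**Timepoint percentages.** SAP 3.3 does not say how they are computed. They follow the Kaplan-Meier sentence, so reading them off the curve is plausible, but a crude count over all participants would keep the dead in the denominator and show no inflation.

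**Scope.** A reader might infer that every time-to-event result is inflated, and the slower ADAMTS13 endpoints most of all. The documents do not support that. The censoring rule does cover those variables, but Kaplan-Meier is spelled out in the SAP only for platelet response, and the content of SAP 3.4 on other endpoints is not public.

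**Few deaths.** A reader might apply the 10 to 20% acute mortality in Protocol 2.2, or about 6 to 11 of 55. With every survivor responding, the excess would then be 6/55 = 10.9 to 11/55 = 20.0 points. That figure describes the period before caplacizumab and is not a forecast for this trial. Protocol 2.3.2 reports 2.2% for refractoriness and death combined in a cohort given caplacizumab, immunosuppression and plasma exchange: 0.022 × 55 = 1.2 participants, under a regimen that included plasma exchange. Exclusion E 09 removes severe neurological and cardiac presentations. A death must also precede a response whose median was about 3 days in earlier trials. No death, or one, is plausible.

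**Visibility.** Deaths are reported elsewhere: iTTP-related death is a secondary endpoint, and the safety analyses tabulate deaths by period and cause. This limits the harm but does not correct the curve.

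**Conclusion.** The point stands for time to platelet count response. On the more natural reading, SAP 5.4 censors deaths in a Kaplan-Meier analysis and so overstates cumulative response; on the other reading it is silent on deaths. At N = 55 the overstatement is about 1 to 2 points per death before response, largest when every survivor responds. This rests on an assumed number of deaths, and with none there is no error.

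A reader might infer that the trial's main result is inflated. It is not. The primary endpoint is a proportion in which undetermined remission counts as failure, the other proportion endpoints do not use this rule, and no hypothesis test depends on the curve. The median, which Protocol 9.2.3 names as the summary, hardly changes with 1 to 3 deaths. This is a minor correction, worth making because the rule is written down, errs in one direction only and is easily replaced.

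**What to change.** State in SAP 5.4 that death before the event is a competing event, and keep the last-value rule only for living participants without the event. In SAP 3.3, report the Aalen-Johansen cumulative incidence, with 95% confidence intervals, for the curve and the timepoint percentages of time to platelet count response, and say that the percentages come from it. Do the same for any other variable on the SAP 5.4 list that is analysed by Kaplan-Meier. Do not carry the dead forward as non-responders in a Kaplan-Meier analysis instead, for the reason shown above.

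The cost is a sentence or two in the SAP and standard software, with no new data. The change should be made before the final analysis, so that the rule is not chosen once the deaths are known. If nobody dies before response, the output is identical to Kaplan-Meier.

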5.3 APPENDIX 3 DEMOGRAPHICS AND BASELINE CHARACTERISTICS, PRIOR OR CONCOMITANT MEDICATIONS

Demographics, baseline characteristics, medical surgical history

The following demographics and baseline characteristics, and medical and surgical history will be summarized using descriptive statistics on the mITT and FAS populations.

Demographic and baseline characteristics:

- age at screening visit in years as quantitative variable and in classes (<65, \geq 65 years, and (<75, \geq 75 years)
- gender (Male, Female)
- race (American Indian or Alaska Native, Asian, Black or African American, Native Hawaiian or Other Pacific Islander, White, Not Reported, Unknown)
- ethnicity (Hispanic or Latino, not Hispanic or Latino, Not Reported, Unknown)

Baseline (see definition in [Section 3.1](#)) safety and efficacy parameters (apart from those listed above) will be presented along with the safety and efficacy summaries.

Medical (or surgical) history includes general medical history and iTTP-specific medical history. Medical and surgical history will be coded to a LLT, PT, HLT, HLGT, and associated primary SOC using the MedDRA version currently in effect at Sanofi at the time of database lock.

iTTP-specific medical history includes the description of the previous episodes (initial and recurrent), the number of previous episodes, time since iTTP diagnosis defined by date of

iTTP-specific medical history – date of iTTP diagnosis + 1 day (in year) and if the participant was previously exposed to caplacizumab. This includes also the following characteristics assessed at baseline: ADAMTS13 activity (in quantitative and by class: <10/≥10%), platelet count (in quantitative only), LDH, cTnI, and serum creatinine (for these 3 last parameters: in quantitative and by class: ≤ULN/>ULN), and also Glasgow Coma scale assessment.

Prior or concomitant medications

All medications will be coded using the World Health Organization-Drug Dictionary (WHO-DD) using the version currently in effect at Sanofi at the time of database lock.

- Prior medications are those the participant used prior to first study IMP intake. Prior medications can be discontinued before first administration or can be ongoing during treatment period.
- Concomitant medications are any interventions received by the participant concomitantly to the study IMP during the TE period, ie, up to the last IMP administration + 28 days.

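### SAP 5.4 dates normalization of creatinine and troponin (and LDH) at the first value at or below ULN with no visible condition on baseline, so participants who start normal shorten any pooled time

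*SAP*

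**What the plan says.** SAP 5.4 (Time to event) gives one-line derivations for several marker endpoints. For LDH, creatinine and troponin I, the event is the first date at or below the limit: "ULN for the first time - Date of start of treatment". For the antibody endpoint, with a positivity threshold of 12 U/mL, it is "Date of reduction of anti-ADAMTS13 antibodies below the threshold of positivity - Date of start of treatment". A common rule above these lines covers participants with no event and those who die: "the censoring date will be defined as the last non-missing value of the analyzed parameter". It does not mention participants already at or below the limit when treatment starts.

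SAP 5.3 tabulates baseline LDH, cTnI and serum creatinine "in quantitative and by class: ≤ULN/>ULN", so both classes are expected.

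The same appendix does write start conditions for other endpoints. Sustained clinical response counts from Day 2, and both ADAMTS13 times require that clinical response has come first.

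In the public SAP, section 3.4, on the analysis of other endpoints, survives only as a heading. The Other rows of the objectives tables in the protocol (Section 3) and SAP (1.2) are also blacked out.

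**The concern.** A time to normalization is meaningful only for someone who starts abnormal. If a participant with a normal baseline creatinine is kept in the derivation, the first post-dose value is usually normal too, and an event is recorded at once. That event measures the sampling schedule, not recovery. Pooled with participants who had organ injury, it pulls the estimated time down, and more so as the normal fraction grows.

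This matters because the trial has one arm. With no control group handled in the same way, a short pooled time could be read as fast recovery without first-line plasma exchange when it partly reflects who was enrolled.

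**Working it through.** The plan states no figure for these endpoints, so there is nothing to reproduce. The check asks how far a pooled median moves.

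**Inputs**
- Event rule and absence of a baseline condition: SAP 5.4.
- Both baseline classes foreseen: SAP 5.3.
- Planned mITT size of 55: SAP 4 (illustration only).
- Fraction f at or below ULN at baseline: not in the documents. Assumed range 5% to 50%.
- Median recovery time m among those abnormal at baseline: not in the documents. The ratio below does not depend on it; 5 days is used for illustration.

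**Formula.** Let G(t) be the distribution of recovery time among those abnormal at baseline. If a fraction f has the event at once and nobody is censored, the pooled distribution is f + (1 − f)G(t). Setting this to 0.5 gives G(t) = (0.5 − f)/(1 − f). So for any recovery distribution, the pooled median is only that quantile of true recovery. With exponential recovery, G(t) = 1 − 2^(−t/m), and the pooled median is m × [1 + log2(1 − f)], or zero once f reaches 0.5.

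| f | Normal, of 55 | Quantile of true recovery | Pooled median / m | If m = 5 days |
|---|---|---|---|---|
| 5% | 2.8 | 0.474 | 0.926 | 4.6 |
| 10% | 5.5 | 0.444 | 0.848 | 4.2 |
| 25% | 13.8 | 0.333 | 0.585 | 2.9 |
| 40% | 22.0 | 0.167 | 0.263 | 1.3 |
| 50% | 27.5 | 0 | 0 | 0 |

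The shortening is therefore 1 − 0.926 = 7%, 1 − 0.848 = 15% and 1 − 0.585 = 41% (rounded) at 5%, 10% and 25% normal. A simulation with n = 55, m = 5 days and 4,000 runs gave mean pooled medians of 4.7, 4.3, 3.0, 1.4 and 0.4 days for the five rows, against about 5.1 days among those abnormal at baseline.

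In practice the floor is the first draw rather than zero. SAP 5.4 uses central values, with local values only as substitutes, and Protocol 1.3.4 sends the first post-baseline sample to the central laboratory at 24 hours. Placing the early events at day 1 leaves the 5% to 40% rows unchanged, because each of those medians is later than day 1.

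**By marker**
- *Creatinine*: inclusion criterion I 02 asks for largely intact kidney function. The numerical limit in the French score is 2.27 mg/dL rather than ULN, and no proportion at or below ULN is given. A sizeable f is plausible but not shown.
- *Troponin*: Protocol 2.2 says "Elevations of serum troponin I and troponin T are common", which is not universal, and exclusion E 09 removes values above 5×ULN. A moderate f is possible. The troponin formula in SAP 5.4 also repeats the creatinine wording ("Date where serum creatine"), a separate slip.
- *LDH*: Protocol 2.2 says "Most patients have very high levels of lactate dehydrogenase (LDH", so f should be near the bottom of the table.
- *Antibody*: a reduction below the threshold implies a start above it, so only explicit wording is lacking.

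**Baseline draws after a marketed dose.** SAP 3.1 defines baseline as the last value before the first study dose, including for participants given marketed caplacizumab beforehand. SAP 5.4 starts the clock at the first caplacizumab dose of either kind and takes the median of all values in the first 24 hours. For these participants, a baseline sample drawn after the marketed dose falls inside that window and can help to define the event.

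**The case against.** The strongest objection is the redaction. These times are not among the listed secondary endpoints, so their analysis belongs in SAP 3.4, which cannot be read. SAP 5.4 is an appendix of date formulas. Even for time to platelet response it names no population, which is given in SAP 3.3. Silence in 5.4 is therefore not proof that everyone is included. This stands, and it limits the point to the visible derivation.

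It does not remove the point. A programmer works from 5.4, which writes start conditions where it wants them and has none here.

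A reader might infer more than the documents support:
- *That these times are derived for all participants and reported as Kaplan-Meier medians.* The protocol gives Kaplan-Meier for time-to-event endpoints, but under secondary analyses. The visible statements about medians concern platelet response only.
- *That all four markers are equally affected.* LDH is very high in most patients, and the antibody wording already implies a positive start.
- *That delayed recovery could not be seen.* SAP 3.6.3.1 summarizes results and changes from baseline by timepoint for creatinine, LDH and cTnI, and reports abnormalities by baseline status. The later part of any curve would also remain visible.
- *That the median will collapse to the first draw.* That needs at least half normal at baseline, which the documents do not show for any marker.

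The daily windows in 5.4 start at the first dose, so they already exclude ordinary pre-dose baselines. The exception is a baseline drawn after a marketed dose.

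**Conclusion.** The point holds for the visible text. As written in SAP 5.4, a participant who starts at or below ULN has an event at the first draw for creatinine, for LDH, and for troponin once its formula refers to troponin. The SAP itself expects such participants.

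The shortening in the table rests on an assumed normal fraction, exponential recovery, no censoring, and a median being the statistic reported. The quantile column does not need the exponential assumption. The consequence could be material for creatinine, is possible for troponin, and is likely to be small for LDH. It disappears if SAP 3.4 already restricts the analyses. The endpoints are descriptive and untested, so the primary analysis, the listed secondary analyses and the sample size are untouched.

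**What to change.** In SAP 5.4, state that each time-to-normalization analysis includes only participants whose baseline value is above 1×ULN. For the antibody endpoint, make explicit that baseline is 12 U/mL or higher. Report the number included and the number already normal at baseline. Count only values taken after the baseline sample, which matters where marketed caplacizumab preceded the baseline draw. Correct the troponin formula at the same time. If SAP 3.4 already sets the restriction, a cross-reference in 5.4 is enough.

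The cost is a sentence or two, with no new data. The downside is a smaller n, mainly for creatinine and troponin: of 55 participants, about 41 would remain if 25% were normal at baseline (55 × 0.75), and 27 or 28 if half were.
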